### **Outcome Analysis**

In order to evaluate whether tailored DCS administration produces superior outcomes to pre-session DCS, post-session DCS, and placebo, we will examine if the dummy variable contrasting tailored DCS to the relevant comparison condition is a significant predictor of the intercept. We will alternately "center" the "assessment week" variable at either posttreatment, 1-mo FU, or 3-mo FU to test for significant differences between conditions at each of these time points.

We will also examine a number of possible moderators of the potential superiority of tailored DCS over the comparison conditions (and, secondarily, of the superiority of pre-and post-DCS administration over PBO). We will use the Fournier approach to identify important moderators. This approach uses an algorithmic method to select significant predictors and moderators within each group of potential moderators (e.g., demographics, clinical and personality characteristics). These selected moderators are then combined in a final analysis, which identifies moderators that are significant over and above the other potential moderators. This approach strikes a balance between testing each moderator separately (which substantially increases Type I error due to the multiple tests) and testing all moderators simultaneously (which may substantially increase the likelihood of Type II error).

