## Methods

### Study Design and Objectives

The primary objective of this study is to optimize the application of DCS to augment exposure therapy. We will examine the relative efficacy of tailoring post-session administration of DCS based on end fear levels during a five-session exposure therapy protocol for SAD. Tailored post-session DCS administration will be compared to the most common application of DCS in prior research, which is unselective DCS administration before exposure sessions, as well as unselective post-session DCS administration in order to determine whether post-session DCS administration needs to be tailored. We will also include a placebo condition. We hypothesize that selectively administering DCS when fear levels are low at the end of exposures will lead to greater reductions in social anxiety symptoms at post-treatment and follow-up compared to placebo, unselective pre-session DCS administration, and unselective post-session DCS administration.

A secondary aim is to examine whether DCS enhances fear extinction retention in a laboratory setting. Doing so will allow us to make inferences about the mechanism of action through which DCS enhances outcomes (i.e. whether its effects are due to increased fear extinction retention), and to better interpret any possible null results of the clinical trial (e.g. DCS may work in an experimental paradigm but not in a clinical setting). To examine the effect of DCS on fear extinction retention, a subset of participants will complete a computerized protocol involving a fear conditioning procedure, fear extinction training, and fear extinction retention testing on three separate days, while receiving DCS or pill placebo prior to extinction training. We hypothesize that participants receiving DCS will show greater fear extinction retention in the laboratory experiment than those receiving placebo.

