## **Screening and Randomization**

Individuals interested in the study will undergo a psychiatric evaluation to evaluate psychiatric inclusion and exclusion criteria. Participants will be medically cleared by a study physician.

Participants in the optional fear extinction retention experiment will be randomized to receive either DCS or placebo prior to fear extinction procedures. For the clinical trial portion of the study, participants will be randomized to one of four conditions: 1) tailored post-session DCS, 2) unselective pre-session DCS, 3) unselective post-session DCS, or 4) pill placebo. The conditions of the fear extinction experiment will be equally distributed across the four clinical trial conditions such that participants will be equally likely to receive any combination of fear extinction condition and trial condition. Randomization will occur by site using variable-sized permuted block randomization (block sizes varying from 4 to 12). Randomization tables will be created before the first subject is run and sent to the study pharmacist to make the appropriate medication kits. The statistician will check the balance of randomization to control for any unbalanced factors.

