## Data Analysis

We will assess the equivalence of the treatment groups on key baseline variables and any variables that differ among groups will be used as covariates in the final analyses. We will examine missing data patterns, dropout rates, and distributional properties of measures and use transformations to improve distributions if necessary. We will use pattern mixture modeling to assess the effect of missing data. We will rerun our analyses coding for various missing data patterns (no missing data, sporadic

missing, dropouts, etc.) to determine 1) if missingness impacts our findings and 2) how the differences between treatment conditions depends on the missing data pattern.

We will use multilevel modeling (MLM) to evaluate the effect of condition on our continuous outcome measures (LSAS, SPD-SC severity, MADRS, QLES-Q) and generalized linear mixed modeling (GLMM, which is MLM with a logistic linking function) to examine DCS's effect on the dichotomous outcomes ("response" and "remission," explained below). MLM is the recommended method for analyzing longitudinal psychiatric data, easily accommodates missing data, and allows inclusion of all subjects in the analysis even if they drop out. In our MLM analyses, the repeated assessments over time will be nested within individuals, which will be nested within treatment cohort, thereby appropriately accounting for correlated scores within cohorts. We will use a piecewise growth curve model, separately modeling change over time during treatment and follow-up. We will test for quadratic trends and include them if significant. Other non-linear models (e.g., exponential models) will be also be tested, and the model that best fits the data (based on AIC and BIC) will be used. Our "time" variable in these models will be coded as "assessment week" and will reflect the number of weeks since baseline. Using this model, we can test differences between tailored DCS administration and the 3 comparison groups (pre-session DCS, post-session DCS, and placebo) by including 3 dummy coded variables as predictors of the growth curve parameters. Each dummy variable will contrast tailored DCS to each of the other 3 conditions.

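### Baseline LSAS and SPD-SC enter the model only if the arms are found to differ, by an undefined rule; pre-specified adjustment would gain precision at almost no cost

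*Combined protocol and SAP*

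**What the plan says.** The hypothesis in Study Design and Objectives is that tailored DCS "will lead to greater reductions in social anxiety symptoms at post-treatment and follow-up". The Data Analysis section specifies a piecewise multilevel growth model whose time variable "will reflect the number of weeks since baseline". The arms are compared "by including 3 dummy coded variables as predictors of the growth curve parameters". The Outcome Analysis section then re-centres the time "variable at either posttreatment, 1-mo FU, or 3-mo FU to test for significant differences between conditions at each of these time points", and at each centring "we will examine if the dummy variable contrasting tailored DCS to the relevant comparison condition is a significant predictor of the intercept". Each primary contrast is thus a difference in fitted level at one time point. Neither section mentions a baseline covariate or a constraint that the arms share a baseline mean.

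Two sentences deal with covariates. Data Analysis: "We will assess the equivalence of the treatment groups on key baseline variables", after which "any variables that differ among groups will be used as covariates in the final analyses". Screening and Randomization: "The statistician will check the balance of randomization to control for any unbalanced factors". Neither gives a test, a significance level, a size of difference or a list of variables. LSAS and SPD-SC are not named as variables to be checked. Table 3 schedules both at screening and at baseline.

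**The concern.** If each arm has its own fitted starting level, a chance gap at baseline passes into the later contrasts in proportion to the baseline-outcome correlation. Having baseline as week 0 of the outcome does not remove this. The plan does not say whether baseline is an outcome row or a covariate, so free arm-specific baselines are an inferred reading, though the natural one when the arm dummies predict the growth parameters.

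Two things are at stake. One is avoidable variance, and a contrast that is off-centre given the imbalance actually observed. The other is reproducibility: two statisticians who read the word differ in two ordinary ways would fit different primary models to the same data, and the choice would be made after the data are seen.

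**Working it through.** **Inputs from the documents.** N = 156 in four arms (39 per arm; equal allocation is implied, not stated as a ratio). Detectable effect d = .296, or 6.59 LSAS points, at power .80 (Power analysis). The implied LSAS SD is 6.59/.296 = 22.3.

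**Assumed.** Two-sided alpha .05; baseline-outcome correlation rho = .3, .5 or .7. The variances and covariances used in the power software are not reported, so rho cannot be derived. The LSAS ≥ 60 entry criterion (Table 1) may push it towards the low end.

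**The plan's own figure.** A plain comparison of 39 with 39 at d = .296 has power 25.7%; 80% would need 180 per arm. The figure of .296 is not reproduced here, but without its inputs it cannot be shown wrong. It is a separate question.

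**Gain from always adjusting, single time point.** The variance factor is 1 − rho². Equivalent sample size per arm is 39/(1 − rho²), and detectable d is 2.80 × √(2(1 − rho²)/39), against 2.80 × √(2/39) = .63 unadjusted.

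| rho | variance cut | equivalent per arm (total) | detectable d | power for 6.59 points (unadjusted 25.7%) |
|---|---|---|---|---|
| .3 | 9% | 42.9 (171) | .61 | 27.6% |
| .5 | 25% | 52.0 (208) | .55 | 32.4% |
| .7 | 49% | 76.5 (306) | .45 | 44.6% |

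The power column includes the small-sample penalty √(1 + 1/149) = 1.003. At rho = 0 that penalty is the whole cost: a 0.3% larger standard error.

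**What the stated rule delivers.** Simulation with 4 × 39 patients, one outcome time point, a true d = .5 (chosen for illustration) and 20,000 runs per cell. The rule was read in several ordinary ways.

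| Reading of the rule | trials that adjust | power, rho .3 | rho .5 | rho .7 |
|---|---|---|---|---|
| never adjust | 0% | .595 | .595 | .593 |
| four-arm ANOVA p < .05 | 5% | .596 | .602 | .610 |
| any of three pairwise p < .05 | 12–13% | .599 | .612 | .632 |
| any standardized difference > .2 | 71% | .622 | .678 | .795 |
| any standardized difference > .1 | 95% | .630 | .705 | .854 |
| always adjust | 100% | .632 | .711 | .867 |

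Type I error was .049–.051 unadjusted, .048–.051 always adjusted and .035–.049 under the rule.

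**Does week 0 in the growth model already adjust?** This was checked by generalized least squares on a piecewise model with complete data, assumed visit weeks, a between-person variance share of .7, a separate baseline mean and nine visits. With free arm baselines the detectable d at post-treatment is .578 whatever the baseline correlation. With a common baseline mean it is .574, .546, .483 and .370 at correlations .1, .3, .5 and .7. With seven visits the figures are .590 free and .586, .558, .497 and .388 common. A second set of assumed variance components, with random slopes and baseline-to-post correlations of .40 to .74, gave a 9% to 38% smaller standard error under the common mean. So week 0 as an outcome row does not by itself adjust.

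**In LSAS points.** The chance gap between two arms has standard error SD × √(2/39): 3.40 for a baseline SD of 15 (assumed) and 5.05 for 22.3. With equal SDs at baseline and outcome, rho times the gap is carried into the contrast. A 1-SE gap therefore shifts it by 1.0–1.5, 1.7–2.5 or 2.4–3.5 points at rho .3, .5 or .7. A gap of 6.59 points would shift it by 2.0, 3.3 or 4.6.

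**The case against.** The strongest reply is that nothing here is invalid. Randomization makes expected baseline means equal, so a difference in level at post-treatment estimates the difference in reduction. Type I error is not inflated. This stands, and the level-versus-reduction wording is not itself a defect. What remains is lost precision and an undefined rule.

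The gain rests on a correlation that nobody outside the trial can see. That also stands. At a correlation of .1 the detectable d moves only from .578 to .574. The cost of adjusting there is equally negligible, so the recommendation does not depend on rho, but its benefit does.

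The power table is for a single time point and a chosen effect, not the planned model. That is fair, but the repeated-measures check shows the same pattern at slightly different levels (.578 unadjusted instead of .63).

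A 6.59-point gap is .44 SD (SD 15) or .30 SD (SD 22.3), so a standardized-difference trigger of .2 would already catch it, provided LSAS is checked. This is true. Under a p-value reading the same gap, compared between two arms, gives about p = .052 or .19 and would be missed, so the outcome depends on which reading is used. The 22.3 is an implied outcome scale used as an upper bound, not a reported baseline SD.

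Finally, a baseline-covariate model drops participants who have only a baseline score, whereas the Power analysis section counts everyone with at least one data point. This is correct, and it is a reason to prefer the common-mean form, which keeps them.

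**Conclusion.** The concern holds. The plan leaves baseline adjustment of its primary contrasts to an undefined, data-driven rule, and always adjusting is a better method that can be specified now. Under assumed correlations of .3 to .7 it is worth 9% to 49% of the variance of each contrast. If the rule means a four-arm test at p < .05, almost none of that is recovered: at rho .5, power for d = .5 is .602, against .711 always adjusted and .595 never adjusted. The conclusion rests on the inferred reading that arm baselines are free, and its size rests on a rho that the documents do not report. It is a matter of efficiency and reproducibility, not bias, so it should be changed but does not undermine the trial. Adjustment alone does not bring a 39-versus-39 contrast down to the stated d = .296 at these correlations.

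**What to change.** State in the Data Analysis and Outcome Analysis sections that LSAS and SPD-SC severity are adjusted for their own baseline in every case, at post-treatment, 1 month and 3 months. Choose one form and name it:

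- keep baseline as an outcome row, constrain all four arms to a common mean there, and test the arm difference at each time point (preferred, because participants with only a baseline score stay in); or
- use the baseline score of that outcome as a fixed covariate, with only post-baseline scores as outcomes.

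Do not use baseline in both roles. Say whether the screening or the baseline assessment supplies the score, since Table 3 has both. Remove the rules in Data Analysis and in Screening and Randomization that select covariates by observed imbalance; a balance check may stay as a description of the randomization. If further covariates are wanted, list them now on prognostic grounds.

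The cost is analysis-plan wording, with no new data. Because the trial is described as ongoing, the change should be dated and fixed before unblinding.

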### **Power analysis**

This study is not powered to detect small differences between treatment conditions, nor is it powered to detect differences on our dichotomous outcomes. We performed power analyses only for our primary outcomes, which were continuous measures of LSAS and SPD-SC. MLM allows the inclusion of all subjects with at least one data point, regardless of missing data and regardless of whether they drop

out. Thus, we based our power analysis on 156 participants and conservatively assumed that, on average, we will obtain 5 out of the 7 total assessments from each subject. The power analyses were calculated using the program PinT 2.12 (Power in Two Level Models).

For our main outcome analysis, we used our similarly sized DCS trial to estimate the variances and covariances required by PinT, and calculated detectable effect sizes for both LSAS and SPD-SC. PinT indicated we would have a power of .80 to detect an effect size as low as  $d=.296$ , between a small ( $d=.20$ ) and a medium ( $d=.50$ ) effect size. This translates into a difference of 6.59 points on the LSAS and .42 points on the SPD-SC (at post-treatment, 1-month follow-up, or 3-month follow-up). For the Fournier moderator analysis, we assumed five simultaneous moderators in each group, and included their 15 interactions with the 3 dummy variable contrasts. Moderators were modeled as predictors of both the intercept and slope. Using our prior DCS study to calculate the variances and covariances required by PiNT, we found that, with .80 power, we could detect an effect size of  $d=.466$ , slightly smaller than a medium effect size.

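### Each comparison of tailored DCS with another arm is tested six times (two unranked primary outcomes at three visits), and the plan does not say which test decides it

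*Combined protocol and SAP*

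**What the plan says.** All references are to the combined protocol and SAP.

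- **Contrasts.** Data Analysis enters three dummy variables: "Each dummy variable will contrast tailored DCS to each of the other 3 conditions".
- **Criterion.** Outcome Analysis asks whether the relevant dummy variable "is a significant predictor of the intercept". It gives no alpha level and no sidedness.
- **Visits.** The time variable is centred in turn at post-treatment, 1 month and 3 months "to test for significant differences between conditions at each of these time points". No visit is named as primary.
- **Outcomes.** Power analysis refers to "our primary outcomes, which were continuous measures of LSAS and SPD-SC". Table 3 also lists both under its primary heading, without order. The detectable difference is given for either scale "at post-treatment, 1-month follow-up, or 3-month follow-up", so this section does not single out an outcome or a visit either.
- **Hypothesis.** Study Design and Objectives expects tailored DCS to do better than all three other arms, both at post-treatment and at follow-up. It does not say whether all of these results must be significant, and it does not mention the two scales.
- **Error control.** Type I error is raised only for moderators, where testing each one separately is described as something "which substantially increases Type I error due to the multiple tests".
- **Model form.** Data Analysis fits growth in two segments, one for the treatment period and one for follow-up. On curvature it says: "We will test for quadratic trends and include them if significant". The same section lets AIC and BIC choose among other growth forms, allows transformations where needed, and takes as covariates any baseline variables that differ between groups.

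**The concern.** The contrasts, outcomes and visits are all specified in advance. What is missing is the rule that turns six results on one contrast into a conclusion about that contrast. Suppose tailored DCS beats unselective post-session DCS on LSAS at 1 month and on nothing else. The plan does not say whether tailoring has then been shown to help.

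The contrast against unselective post-session DCS matters most, because Study Design and Objectives includes that arm to find out whether post-session dosing needs tailoring at all. A lenient rule chosen after the data are seen would raise the false-claim rate on that question. A strict rule would leave much less power than the plan reports. Either way, the same data could support or fail to support tailored DCS.

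**Working it through.** **The plan's own figure.** Power analysis states .80 power at d = .296, or 6.59 LSAS points and .42 SPD-SC points. These imply standard deviations of 6.59/.296 = 22.3 and .42/.296 = 1.42. The .80 itself cannot be reproduced, because the variances and covariances given to PinT are not in the document. Nothing below depends on d = .296. The .80 is taken as the power of each single test.

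**Count.** 2 outcomes x 3 visits = 6 tests per contrast; 3 contrasts x 6 = 18.

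**Assumptions, none of them in the document.**
- Two-sided .05 per test (critical z = 1.96), which is .025 in the direction favouring tailored DCS.
- Equal arms, so contrasts sharing the tailored arm correlate .5.
- Correlation between outcomes of .5, .8 or .9, and between visits of .5, .7 or .9 (nine scenarios).
- Test statistics multivariate normal, with correlation matrix equal to the Kronecker product of the contrast, outcome and visit matrices; 400,000 draws per scenario.
- Two versions of the visits. In one they vary freely. In the other the follow-up segment is linear, so the 1-month value is 2/3 of the post-treatment value plus 1/3 of the 3-month value.

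**Rule A: any of the six may support the claim on one contrast; no true effect.** Limits by hand: with perfect correlation the error is .025; with independence it is 1 − .975^6 = .141. By simulation:

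| Visits | False result favouring tailored DCS, one contrast |
|---|---|
| Linear follow-up | .050 to .085 |
| Free | .057 to .111 |

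Relative to .025, this is .050/.025 = 2 to .111/.025 = 4.4 times the single-test error.

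**Rule B: every result required (a strict reading of the hypothesis).** A contrast with no true effect passes all six of its tests with probability at most .0085, so error is controlled. Joint power over the 18 tests, with every true effect at the value that gives one test .80 power (limits by hand: .80 with perfect correlation, .80^18 = .018 with independence):

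| Visits | Power to win all 18 |
|---|---|
| Linear follow-up | .265 to .458 |
| Free | .184 to .416 |

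Larger true effects would raise these figures.

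**One outcome and one visit fixed in advance.** Each contrast is a single test, with favourable error .025 if the model is also fixed. The power to win all three contrasts is .612 when each has .80 and the contrasts correlate .5; independence would give .80^3 = .512.

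**The case against.** Several objections have force.

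*The headline could be 18 tests.* A reader might infer that the error to quote is the chance that any of the 18 tests falsely favours tailored DCS, about .12 to .25 under the same assumptions. The document does not support that. It nowhere says that any one significant result counts as success for the trial, and its hypothesis points the other way, to all three arms. The defensible figure is the one for a single contrast.

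*The arms need no joint adjustment.* This largely stands. Study Design and Objectives gives the comparators different purposes: pre-session DCS is the usual earlier practice, unselective post-session DCS tests the need for tailoring, and placebo is the control. Whether to adjust across distinct planned questions is a matter of choice. It does not answer the six tests within each question.

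*The hypothesis already requires winning everywhere.* It can be read so, and then false-positive inflation disappears. But it is a hypothesis, not a success rule, and the power section reports only .80, not the joint power that this reading implies. One could also set the hypothesis against the wording of the analysis and power sections, which link the visits by alternatives. That contrast is weak: those sentences describe where time is centred and what difference is detectable, not what counts as success.

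*This is an early-stage trial.* The Abstract calls it a first step. However, the aim of estimating effect sizes is stated only for response and remission. For the continuous outcomes the plan sets significance tests and a power calculation.

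*The figures rest on assumptions.* They do, and so they are given as ranges. The count of six and the missing rule do not depend on them.

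**Conclusion.** The concern holds, contrast by contrast. The plan provides six tests for each comparison of tailored DCS with another arm and no rule for choosing among them. If any of the six may support the claim, the false-favourable rate is about .05 to .11 instead of .025. If all results are required, error is controlled and joint power is about .18 to .46 when each test has .80. Both ranges assume two-sided .05 per test, equal arms and outcome and visit correlations of .5 to .9.

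Two further inferences should not be drawn. Naming an outcome and a visit does not by itself guarantee .025, because Data Analysis still lets the data choose the growth form, transformations and covariates. And failure to reproduce d = .296 does not show that it is wrong; the inputs are simply not given, and that is a separate matter.

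This should be corrected, but it does not undermine the design: a short addition to the plan settles it.

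**What to change.** Before unblinding, amend Outcome Analysis as follows.

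1. Name one primary outcome and one visit as decisive for each contrast. The choice is the trial team's. LSAS at post-treatment is only an example; the power section covers both scales and all three visits alike.
2. For that test, fix the growth form, any transformation, the covariates, alpha and sidedness in advance. With items 1 and 2 together, each contrast returns to about .025 in the favourable direction at two-sided .05.
3. State whether the three contrasts are separate questions, each reported at two-sided .05, or one joint claim of beating all three arms. The joint claim needs no alpha adjustment, but its power should be reported (about .61 if each contrast has .80). Holm or a fixed sequence across arms is optional.
4. Report the other primary outcome and the other visits as secondary, with confidence intervals.

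**Cost.** No extra data or participants are needed. The Abstract describes the trial as ongoing, so this is a plan amendment, and the DSMB section has that board review proposed protocol amendments. The secondary outcome and visits can no longer support a confirmatory claim. If the team opts for Holm, its strictest step (.05/3, critical z 2.394) lowers the power of a contrast that has .80 at two-sided .05 to about .66: 1.960 + .842 − 2.394 = .408, and the normal probability below .408 is .658.
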